2.2.1. EFFICACY/PHARMACODYNAMIC ASSESSMENTS

The efficacy/pharmacodynamic endpoints include:

- Change (absolute and percent change) from baseline in PN/IV support (volume and calories), citrulline (only for the cohort of children 1-15 years of age), and enteral nutritional support (volume and calories), separately, at each visit
- Reduction in PN/IV volume of at least 20% at week 24 (or EOT) compared to baseline
- 100% reduction in PN/IV volume (complete weaning of PN/IV support) at week 24 (or EOT) compared to baseline
- ≥20% reduction in PN/IV volume at each visit
- Change (absolute and percent change) from week 24 (or EOT) in PN/IV support (volume and calories), citrulline (only for the cohort of children 1-15 years of age), and enteral nutritional support (volume and calories), separately, to week 28 (or EOS)
- Change in hours per day and days per week of PN/IV support

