6.3. HANDLING OF DROPOUTS OR MISSING DATA

All subjects in the analysis population defined in Section 7 will be included in the associated analyses.

No imputation for missing data (e.g., last observation carried forward [LOCF]) will be applied except for the partial dates for adverse events and prior/concomitant medications.

Details on how to handle partial dates for adverse events and prior/concomitant medications are described below.

Complete dates will be imputed from partial dates of adverse events and medications solely for the purpose of defining treatment emergence for adverse events and prior/concomitant status for medications (Imputed dates will not be presented in the listings). Dates will be defined using the hierarchy of derivations below.

Adverse event or medication start date (references to month and year are the month and year of the start date):

- 1. If year and month are known, and it is the month and year of the first dose date, use the first dose date.
- 2. If year and month are known, and it is not the month and year of the first dose date, use the first day of the month.
- 3. If only year is known, and it is the year of the first dose date, use the first dose date.
- 4. If only year is known, and it is not the year of the first dose date, use the first day of the year (1st January).
- 5. Should any of the previous start dates created be after a complete stop date provided, use the stop date as the start date, instead of the date that would otherwise be created.
- 6. For medication start date, if "Before Informed Consent" is ticked then use the date of informed consent.
- 7. Otherwise, if start date is unknown leave as missing.

Adverse event or Medication stop date (references to month and year are the month and year of the stop date):

Document: T:\Shire\Teduglutide\XXA39799\Biostatistics\Documentation\SAP\SHP633-302 SAP Final

1.0 17Apr2019.docx

Version Number: Version Date: Final 1.0 17Apr2019

Reference: CS WI BS005

Author:

Template No: CS TP BS016 Revision 4

Effective Date: 01Apr2016

- 1. If year and month are known, use the last day of the month.
- 2. If only year is known, use the last day of the year (31st December).
- 3. Otherwise, if stop date is unknown leave as missing.

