- Total estimated remaining small intestinal length (cm)
- Presence of the distal/terminal ileum (Y/N) and ileocecal valve (Y/N)
- Method to determine remaining anatomy length (surgery, radiology, other)

For children 1-15 years of age, duration of SBS in years will be calculated as (Date of informed consent form signed – Date of diagnosis of SBS +1) / 365.25 and rounded to 1 decimal place for reporting.

For infants, duration of SBS in months will be calculated as (Date of informed consent form signed – Date of diagnosis of SBS +1) / (365.25/12) and rounded to 1 decimal place for reporting.

The following Parenteral Nutrition/Intravenous History and Enteral Nutrition (EN) History information collected at the Baseline visit will be summarized with descriptive statistics defined in Section 6.1 for the ITT and Safety populations:

- Years or months since start of PN/IV dependency
- Current use of EN (Y/N), reason not taking EN (following a regular diet, other)
- Years or months since start of EN dependency

For children 1-15 years of age, years since start of PN/IV dependency will be calculated as (Date of informed consent form signed – Start date of PN/IV dependency +1)/365.25.

For infants 4-12 months corrected gestational age, months since start of PN/IV dependency will be calculated as (Date of informed consent form signed – Start date of PN/IV dependency +1)/ (365.25/12).

Years and months since start of EN dependency will be calculated in a similar manner but using the start date of EN dependency. Both these durations will be rounded to 1 decimal place for reporting.

The following Parenteral Nutrition/Intravenous History information collected at baseline will be summarized in the by-visit efficacy tables and listed:

Document: T:\Shire\Teduglutide\XXA39799\Biostatistics\Documentation\SAP\SHP633-302 SAP Final

1.0_17Apr2019.docx

Template No: CS_TP_BS016 Revision 4

Effective Date: 01Apr2016

Author:

Version Number: Version Date:

Reference: CS_WI_BS005

Final 1.0

17Apr2019

- Prescribed weekly PN/IV volume
- Prescribed weekly PN/IV calories
- Prescribed number of days per week of PN/IV
- Prescribed average number of hours per day of PN/IV
- Prescribed weekly EN volume
- Prescribed weekly EN calories

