If more than 2 days' values in a week are missing, the average daily value will not be calculated and will be assigned as missing. If more than 5 days' values in two weeks before baseline visit, the baseline values are missing. These missing data handling rules will be used to calculate all other diary average diary parameters, including PN/IV calories, PN/IV hours per day, PN/IV days per week, EN volume, and EN calories.

Document: T:\Shire\Teduglutide\XXA39799\Biostatistics\Documentation\SAP\SHP633-302 SAP Final

__1.0__17Apr2019.docx

Version Number: Version Date: Final 1.0 17Apr2019

Author:

Template No: CS_TP_BS016 Revision 4

Effective Date: 01Apr2016

Reference: CS_WI_BS005

Percent reduction in weight-normalized diary and prescribed PN/IV volume from baseline at the scheduled visit will be calculated using the formula below:

% reduction in PN/IV volume at the visit = [(average daily value at the scheduled visit - average daily value at baseline) / average daily value at baseline] * 100

Percent reduction calculation will be performed on both diary and prescribed PN/IV volume data.

Change and percent change from baseline in PN/IV and EN support

The absolute and percent change from baseline in average daily values for PN/IV and EN support (volume and calories) to each scheduled visit during the 24-week treatment period, as well as at EOT and the follow-up period (Week 25, 26, 27, 28), will be presented using descriptive statistics defined in Section 6.1. For EN summary, change from baseline will only be calculated for subjects who took any EN at baseline.

Mean ± SE plots of percent change in PN/IV and EN support (volume and caloric intake) will be generated.

Plots of PN/IV and EN support (volume and caloric intake) by visit will be presented for each individual subject in the ITT population.

95% confidence intervals of the mean will be generated for Week 20 and Week 24/EOT.

Change and percent change from baseline in citrulline

The absolute and percent change in citrulline from baseline to each scheduled visit during the 24-week treatment period, as well as at EOT and the follow-up period (Week 28), will be presented using descriptive statistics defined in Section 6.1 for the cohort of children 1-15 years of age.

≥ 20% Reduction in PN/IV volume at each study visit

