PN/IV volume reduction at each study visit compared to baseline will be calculated using average daily values. The number and percentage of subjects who achieve at least a 20% reduction in PN/IV volume will be presented at each scheduled visit during the 24-week treatment period, as well as at EOT and the follow-up period (Week 25, 26, 27, 28).

Complete weaning off PN/IV support at EOT

A subject will be considered to have achieved independence from PN/IV support (completely weaned off PN/IV) if the investigator prescribes no PN/IV (volume and calories) and there is no use of PN/IV (volume and calories) recorded in the subject diary during the 7 days prior to EOT. The number and percentage of subjects who completely wean off PN/IV support up to EOT will be presented. A listing will present the study week when complete wean off was first achieved for these subjects who completely wean off PN/IV support at EOT.

Change and percent change from EOT in PN/IV support, citrulline, EN support at EOS

Document: T:\Shire\Teduglutide\XXA39799\Biostatistics\Documentation\SAP\SHP633-302 SAP Final

1.0_17Apr2019.docx

Version Number: Final 1.0 Version Date: 17Apr2019

Reference: CS WI BS005

Template No: CS_TP_BS016 Revision 4

Effective Date: 01Apr2016

Author:

Copyright © IQVIA. All rights reserved.

The absolute and percent change from EOT to EOS in average daily values for PN/IV and EN support (volume and calories) as well as citrulline (only for the cohort of children 1-15 years age) will be presented using descriptive statistics defined in Section 6.1. If subject has weaned-off PN/IV or EN at EOT, change from EOT for those parameters will not be calculated.

Change and percent change from baseline in hours per day and days per week of PN/IV support

Change and percent change from baseline in hours per day and days per week of PN/IV support to each visit during 24-week treatment period, as well as at EOT and the follow-up period (Week 25, 26, 27, 28), will be presented using descriptive statistics defined in Section 6.1.

Hours per day of diary PN/IV support for all visits except the baseline visit will be calculated as follows:

Hours per day of diary PN/IV support = (sum of hours per day for each day that PN/IV intake data is recorded within the 7 days prior to the visit / number of days that PN/IV hours per day data is recorded within the 7 days prior to the visit)

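### Absolute change is dropped along with percent change when the starting value is zero, so the EOT-to-EOS table omits every weaned subject and the EN change tables omit anyone who starts EN

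*SAP*

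**What the plan says.** SAP Section 2.2.1 lists as an endpoint "Change (absolute and percent change) from week 24 (or EOT) in PN/IV support (volume and calories"), together with citrulline and EN support, to week 28 or EOS. No subject is excepted there.

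Section 11.1 repeats the endpoint as "The absolute and percent change from EOT to EOS in average daily values for PN/IV and EN support (volume and calories") and then restricts it: "If subject has weaned-off PN/IV or EN at EOT, change from EOT for those parameters will not be calculated". For change from baseline the same section says: "For EN summary, change from baseline will only be calculated for subjects who took any EN at baseline". Neither restriction separates absolute from percent change, and no reason is given for either.

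Weaning off PN/IV at EOT is defined in Section 11.1. The investigator must prescribe none, and "there is no use of PN/IV (volume and calories) recorded in the subject diary during the 7 days prior to EOT". Weaning off EN is not defined.

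Section 6.3 states the general rule: "All subjects in the analysis population defined in Section 7 will be included in the associated analyses". Section 7.2 makes the ITT population primary for efficacy.

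**The concern.** A percent change from zero has no meaning, and leaving it out is correct. An absolute change from zero is simply the later value, so nothing in the arithmetic calls for dropping it.

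The two rules remove different kinds of subject. The EOT rule selects on a post-baseline outcome: for PN/IV it removes exactly those who reached the best result the SAP defines. The table devoted to change after treatment stops then cannot show whether weaning held or was lost, and no planned table counts the weaned subjects who resume PN/IV. The EN rule selects on a baseline characteristic. Its effect is that a subject who starts EN during treatment appears in no EN change-from-baseline summary at any visit.

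The cohorts are very small. The PK Analysis Plan, Section 5, gives planned minimums of 5 children and 2 infants, so one excluded subject is 20% of the first cohort or 50% of the second.

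**Working it through.** The SAP gives no figure to reproduce here; Section 3 sets the sample size by feasibility. The check is therefore algebra, followed by assumed values.

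**Inputs from the documents.** Cohort minimums are 5 and 2 (PK Analysis Plan, Section 5). A subject weaned off PN/IV at EOT has an EOT value of 0 by the Section 11.1 definition, so that subject's change to EOS is at least 0. A subject without EN at baseline likewise has an EN change of at least 0.

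**Assumed inputs, not in the documents.** The number excluded and all changes in mL/kg/day.

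**Formula.** Let k of n subjects be excluded, with mean change r in those retained and w in those excluded.

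- Mean under the SAP rule: r
- Mean over all subjects: ((n − k)r + kw)/n
- Difference, rule minus all: r − ((n − k)r + kw)/n = (k/n)(r − w)

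Since w ≥ 0, the rule understates the mean change when w > r and overstates it when w < r.

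**PN/IV change from EOT to EOS**

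| n | k | r | w | Rule | All subjects | Rule − all |
|---|---|---|---|---|---|---|
| 5 | 2 | 5 | 0 | 5.0 | (15 + 0)/5 = 3.0 | +2.0 |
| 5 | 2 | 5 | 5 | 5.0 | (15 + 10)/5 = 5.0 | 0.0 |
| 5 | 2 | 5 | 10 | 5.0 | (15 + 20)/5 = 7.0 | −2.0 |
| 5 | 2 | 5 | 20 | 5.0 | (15 + 40)/5 = 11.0 | −6.0 |
| 2 | 1 | 10 | 0 | 10.0 | (10 + 0)/2 = 5.0 | +5.0 |
| 2 | 1 | 0 | 20 | 0.0 | (0 + 20)/2 = 10.0 | −10.0 |

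**EN change from baseline**, 5 subjects, 1 without EN at baseline, the other 4 gaining 10 on average:

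- The non-user stays at 0: rule 10, all (40 + 0)/5 = 8, difference +2.
- The non-user reaches 20: rule 10, all (40 + 20)/5 = 12, difference −2.

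**Agreement with other tables.** PN/IV change from baseline is planned "as well as at EOT and the follow-up period (Week 25, 26, 27, 28), will be presented using descriptive statistics", with no exclusion for weaning. If the same subjects contribute at EOT and Week 28, and Week 28 is the EOS value, then the mean absolute change from baseline at Week 28 minus that at EOT equals the all-subject mean change from EOT to EOS. In the first row of the table a reader would derive 3.0 that way and find 5.0 in the dedicated table; in the fourth row, 11.0 against 5.0. The report could thus carry two different values for what looks like the same quantity.

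**The case against.** The best case for leaving the text alone has four parts.

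- **The rule is explicit and pre-specified.** Change among subjects still on support at EOT is an interpretable conditional summary, and a specific rule may override a general one such as Section 6.3. This stands in part: the conditional summary has a meaning, but it is not the endpoint listed in Section 2.2.1, and the SAP does not label it as conditional.
- **The data are not lost.** Weaned subjects stay in the PN/IV change-from-baseline tables for Weeks 25 to 28, the hours-per-day and days-per-week summaries, the counts of at least 20% reduction, the individual plots for every ITT subject, and the listings. This stands and limits the damage. It does not cure it: a formerly weaned subject who resumes up to 80% of baseline volume still counts as having a reduction of at least 20%. For subjects without EN at baseline, observed EN values by visit and individual plots remain, but no change from baseline.
- **The study is descriptive.** Section 6.1 makes no claims of significance, so no error rate is affected. This stands. It also means that the descriptive tables are the evidence, so their denominators matter.
- **Absence of EN at baseline need not be a failing.** Section 9.1 collects "Current use of EN (Y/N), reason not taking EN (following a regular diet, other"). Such a subject may stay at zero EN throughout. This stands.

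A reader might infer that the rules make the off-drug rebound and the EN gain look smaller than they are, because excluded subjects can only stay level or rise. The documents do not support that. A change of at least zero need not exceed the change in the retained subjects, and excluded subjects who stay at zero while others rise make the rule overstate the mean. Nor does the SAP say that starting EN is a benefit, or that follow-up was designed to test persistence of effect: Section 2.1 describes the contacts after EOT as monitoring of safety and nutritional support.

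**Conclusion.** The point holds at moderate severity. Both restrictions discard a valid absolute change, depart from the unrestricted endpoint in Section 2.2.1, and sit badly with the inclusion rule in Section 6.3. The effect is confined to the dedicated EOT-to-EOS table and the EN change tables; the complete-weaning and at-least-20%-reduction results are untouched.

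The size is (k/n)(r − w), of either sign. In the 5-child illustration the difference between the rule and the all-subject mean runs from +2.0 to −6.0 mL/kg/day; in the 2-infant illustration, from +5.0 to −10.0. These figures rest wholly on assumed changes and assumed numbers weaned. They show that the effect can be large relative to the mean being reported; they do not predict it. If nobody is weaned at EOT and everybody takes EN at baseline, the rules change nothing.

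**What to change.** In Section 11.1:

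1. Calculate the absolute change for every subject with both values, including a zero at EOT or zero EN at baseline.
2. Set only the percent change to not calculable when the reference value is zero, and show n separately for absolute and percent change. Tying the rule to a zero reference rather than to weaned status also removes the need to define weaning off EN for this purpose.
3. Add one row to the EOT-to-EOS table: the number of subjects weaned off PN/IV at EOT who received any PN/IV by EOS.

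If the sponsor also wants the summary restricted to subjects still on support at EOT, it can be kept as an additional, labelled row.

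The cost is SAP wording and one table row, using data already collected. The reported mean change may move either way.

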11. EFFICACY/PHARMACODYNAMIC EVALUATION

11.1. Analysis of Efficacy and Pharmacodynamic Variables

Primary efficacy/pharmacodynamic analyses will be conducted on the ITT population. The PP population will be used for sensitivity analysis purpose.

PN/IV and EN support will be reported in both subject diary data and the investigator-prescribed data in the eCRF. Diary and prescribed PN/IV and EN volume/calories will be normalized to weight in order to facilitate comparability of results across patients in this pediatric population. Data will be summarized at all scheduled visits during the 24-week treatment period and the follow-up period (Week 25, 26, 27, 28). An End of Treatment (EOT) time point will also be added. Data collected at unscheduled time points will be included in the listings but will not be summarized at those unscheduled time points.

Prescribed data are the most recent PN/IV or EN prescription (from either baseline or prescription adjustments) prior to or on the date of visit, captured in the PN/IV or EN history and PN/IV or EN adjustments eCRFs.

Average daily values normalized to weight will be calculated for PN/IV volume, PN/IV calories, EN volume and EN calories as follows:

Average Prescribed daily value = (prescribed weekly value / 7) / last available body weight prior to or on the date of visit

Calculation of post-baseline diary PN/IV and EN parameters (including hours per day and days per week of PN/IV support) will be based on the daily support recorded in subjects' diaries within 7 days prior to the date of each scheduled post-baseline visit. Baseline diary PN/IV and EN parameters will be calculated using the most recent 14 days of diary data collected prior to the first dose, and week 1 calculations will not use any pre-baseline diary data.

Average daily values normalized to weight will be calculated for PN/IV volume, PN/IV calories, EN volume and EN calories as follows:

Average diary daily value = (sum of non-missing daily values in the diary / number of days with non-missing values) / last available body weight prior to the visit

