Prescribed PN/IV hours per day for each visit (including baseline) will be taken from the most recent prescription data prior to or at that visit.

Days per week of diary PN/IV support for all visits except the baseline visit will be calculated as follows:

Days per week of diary PN/IV support = (number of days with non-zero values for PN/IV volume within the 7 days prior to the visit / number of days for which any PN/IV intake data is recorded within the 7 days prior to the visit) * 7

For the week 1 visit, data prior to the baseline visit will not be used for the calculation.

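### Diary days per week of PN/IV support uses volume in the numerator but any PN/IV item in the denominator, so an infusion day with volume left blank can be scored as PN/IV-free

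*SAP*

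**What the plan says.** SAP Section 2.2.1 lists change in days per week of PN/IV support among the efficacy/pharmacodynamic endpoints. Section 11.1 summarises it at each visit, at end of treatment and in follow-up.

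The formula in Section 11.1 is introduced by "Days per week of diary PN/IV support for all visits except the baseline visit will be calculated as follows". Its numerator is the "number of days with non-zero values for PN/IV volume within the 7 days prior to the visit". Its denominator is the "number of days for which any PN/IV intake data is recorded within the 7 days prior to the visit". The ratio is multiplied by 7. No days-per-week formula is written out for baseline, although the section says that baseline diary parameters use the latest 14 days before first dose.

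Three other rules bear on a blank field:

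- The average daily volume or calories in Section 11.1 is the "sum of non-missing daily values in the diary / number of days with non-missing values", then divided by body weight. A blank drops out of both counts.
- The missing-day rule in Section 11.1 reads: "If more than 2 days' values in a week are missing, the average daily value will not be calculated and will be assigned as missing". It is then extended: "These missing data handling rules will be used to calculate all other diary average diary parameters". Days per week is named in the list that the sentence goes on to give. The rule does not say which diary field has to be blank for a day to count as missing.
- Section 6.3 says "No imputation for missing data (e.g., last observation carried forward [LOCF]) will be applied", with an exception only for partial dates of adverse events and medications.

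**The concern.** A proportion of days needs one set of days above and below the line. Here a day qualifies for the denominator on any PN/IV item, but for the numerator on volume alone. A day on which the child was infused, with hours or calories entered and volume left blank, is therefore handled exactly like a day with volume recorded as zero. In effect the blank is set to zero, which does not fit Section 6.3 or the way the same blank is handled in the volume average.

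At a given visit this can only lower the value, and a lower value reads as less need for support. The study is open-label and all subjects receive teduglutide, so there is no comparison arm in which the same recording gap would show. The cohorts are small, so one incomplete diary can shift a mean visibly.

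**Working it through.** The plan gives no worked figure for this endpoint, so there is nothing to reproduce. The check applies the formula as written to assumed 7-day diaries.

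**Inputs.** From SAP Section 11.1: V = days with non-zero volume, A = days with any PN/IV item recorded, and value = 7 × V / A. Assumed: t true infusion days, of which b have hours entered and volume blank; rest days entered as zero; some entry on all 7 days, so A = 7.

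**Formula as written.** V = t − b, so the value is 7 × (t − b) / 7 = t − b. Each blank-volume infusion day costs exactly 1 day per week.

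**Two possible repairs.** (i) Count days with any item above zero and divide by days with any item recorded: 7 × t / 7 = t. (ii) Keep the volume numerator and divide by days with volume recorded: 7 × (t − b) / (7 − b).

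| True days | Blank-volume days | As written | Error | Repair (i) | Repair (ii) |
|---|---|---|---|---|---|
| 7 | 1 | 6.0 | −14.3% | 7.0 | 7.0 |
| 7 | 2 | 5.0 | −28.6% | 7.0 | 7.0 |
| 5 | 1 | 4.0 | −20.0% | 5.0 | 4.67 |
| 5 | 2 | 3.0 | −40.0% | 5.0 | 4.20 |
| 3 | 1 | 2.0 | −33.3% | 3.0 | 2.33 |
| 3 | 2 | 1.0 | −66.7% | 3.0 | 1.40 |

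Repair (ii) can also overstate. If the two rest days of a 5-day schedule are entered as zero hours with volume blank, it gives 7 × 5/5 = 7. The formula as written and repair (i) both give 7 × 5/7 = 5.

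**Missing-day rule.** Read on volume, three or more blank volumes make the week missing, so the loss is at most 2 days per week. Read on any item, hours-only days are not missing and that cap does not apply. A wholly blank day does no harm on a 7-day schedule: with one, 7 × 6/6 = 7; with two, 7 × 5/5 = 7.

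**Effect on a cohort mean.** The PK Analysis Plan, Section 5, gives planned minimums of 5 children and 2 infants. One subject who loses 2 days per week at one visit moves the mean by 2/5 = 0.4 days per week among 5 children, or 2/2 = 1 day per week among 2 infants.

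**Change from baseline.** Assume the same formula is carried over to the 14-day baseline and the child is infused every day, so the true change is 0.

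- 4 blank volumes in 14 days at baseline and 2 in 7 at the visit: 7 × 10/14 = 5 against 5, change 0.
- No blanks at baseline and 2 at the visit: 7 against 5, change −2.
- 4 blanks at baseline and none at the visit: 5 against 7, change +2.

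**The case against.** The strongest objection is that the fault may never arise. It needs a diary that accepts hours or calories with no volume, and the diary form is not shown. SAP Section 5 leaves eCRF design and data validation to the Data Management Plan. A volume field made mandatory whenever hours are entered would remove the problem. This stands as a limit on how often the error occurs, not as a defence of the formula.

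The denominator term is also undefined. The hours-per-day formula in Section 11.1 mentions intake data and hours data separately. That can be read as treating hours as something other than intake, in which case an hours-only day would not enter the denominator. It can equally be read as showing that hours are their own diary item, one of several covered by the word any. A day with calories but no volume could remain a problem on either reading. The ambiguity stands and is itself a reason to fix the text.

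The wide denominator may be deliberate, since it copes with rest days on which volume is left blank. That is fair, and it is why the numerator should be widened and the denominator left alone.

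A reader might infer that the formula produces a false treatment benefit. The documents do not support that. The endpoint is a change, no baseline formula is written, and blanks before treatment would push the change the other way. A reader might also infer that the PN/IV results as a whole are compromised, or that the endpoints must contradict one another. They are separate quantities. Prescribed days per week, average volume, the 20% responder endpoint and the weaning definition do not use this formula, and Section 6.1 makes all analyses descriptive with no claims of significance.

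**Conclusion.** The mismatch is in the text and no other rule in the SAP corrects it. Where an infusion day has hours or calories entered and volume blank, and all 7 days have some entry, the diary value for that visit is 1 day per week too low for each such day. The maximum is 2 days per week if the missing-day rule is read on volume.

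This rests on two assumptions that the documents neither confirm nor exclude: that the diary allows such an entry, and that the denominator term covers items other than volume. The frequency is unknown. A bias towards benefit in the change from baseline needs the further condition that baseline is not understated to the same degree. This is a small correction to one descriptive, diary-based result, worth making because a stated rule misclassifies such days.

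**What to change.** Replace the Section 11.1 formula with: diary days per week = (number of days with PN/IV volume, hours or calories above zero) / (number of days with any of these three items recorded) × 7.

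Write out the same formula for baseline, over the 14-day window. State that, for this parameter, a day counts as missing under the missing-day rule only if none of the three items is recorded.

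Do not instead restrict the denominator to days with a recorded volume. As shown in the working, that can still understate or overstate the value.

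One limit remains: a rest day left wholly blank is still taken as missing, as it is now, so rest days need an explicit entry. The cost is a few lines of SAP text and a small programming change, with no new data.
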